10.4. Appendix 4: Abbreviations

10.4. Appendix 4: Appreviations		
AE	adverse event	
AESI	adverse event of special interest	
ALP	alkaline phosphatase	
ALT	alanine aminotransferase	
AST	aspartate aminotransferase	
BM	bowel movement	
BSFS	Bristol Stool Form Scale	
CBC	complete blood count	
CFR	Code of Federal Regulations	
CC	chronic constipation	
CIC	chronic idiopathic constipation	
DILI	drug-induced liver injury	
DSMB	Data and Safety Monitoring Board	
ECG	electrocardiogram	
eCRF	electronic case report form	
EDC	electronic data capture	
eDiary	electronic diary	
EMA	European Medicines Agency	
EOS	End-of-Study	
EOT	End-of-Treatment	
EU	European Union	
FC	functional constipation	
FDA	Food and Drug Administration	
GC-C	guanylate cyclase subtype C	
GCP	Good Clinical Practice	
GI	gastrointestinal	
HEENT	head, ears, eyes, nose, and throat	
HIPAA	Health Insurance Portability and Accountability Act	
IB	investigator's brochure	
IBS	irritable bowel syndrome	
IBS-C	irritable bowel syndrome with constipation	
ICF	informed consent form	
ICH	International Conference on Harmonisation	
IEC	Independent Ethics Committee	
INR	international normalized ratio	
IRB	Institutional Review Board	
ITT	intent-to-treat	
L	•	

IV	intravenous
IWRS	interactive web response system
LAR	legally authorized representative
mITT	modified intent-to-treat
mRNA	messenger ribonucleic acid
MSP	medical safety physician
ObsRO	observer-reported outcome
PCS	potentially clinically significant
PID	participant identification
PK	pharmacokinetic
SAE	serious adverse event
SAP	Statistical Analysis Plan
SBM	spontaneous bowel movement
SoA	Schedule of Activities
SOC	System Order Class
SUSAR	suspected unexpected serious adverse reaction
TEAE	treatment-emergent adverse event
ULN	upper limit of normal

10.5. Appendix 5: Standard Discontinuation Criteria

CONFIDENTIAL

linaclotide

10.5. Appendix 5: Standard Disco CDISC Submission Value	CDISC Definition
Adverse event	Any untoward medical occurrence in a participant or clinical investigation subject administered a pharmaceutical product and which does not necessarily have a causal relationship with this treatment. An adverse event (AE) can therefore be any unintended sign (including an abnormal laboratory finding), symptom, or disease temporally associated with the use of a medicinal (investigational) product, whether or not related to the medicinal (investigational) product. For further information, see the ICH Guideline for Clinical Safety Data Management: Definitions and Standards for Expedited Reporting (modified from ICH E2A) Synonyms: side effect, adverse experience. See also serious adverse event, serious adverse experience. (CDISC glossary)
Completed	To possess every necessary or normal part or component or step; having come or been brought to a conclusion (NCI)
Death	The absence of life or state of being dead (NCI)
Disease relapse	The return of a disease after a period of remission
Lack of efficacy	The lack of expected or desired effect related to a therapy (NCI)
Lost to follow-up	The loss or lack of continuation of a subject to follow-up
Other	Different than the one(s) previously specified or mentioned (NCI)
Physician decision	A position, opinion or judgment reached after consideration by a physician with reference to subject (NCI)
Progressive disease	A disease process that is increasing in extent or severity (NCI)
Recovery	A healing process and/or an outcome implying relative health. The term is typically used in the context of direct and indirect effects of sickness or injury. (NCI)
Screen failure	The potential subject who does not meet one or more criteria required for participation in a trial
Site terminated by sponsor	An indication that a clinical study was stopped at a particular site by its sponsor (NCI)
Study terminated by sponsor	An indication that a clinical study was stopped by its sponsor (NCI)
Technical problems	A problem with some technical aspect of a clinical study, usually related to an instrument (NCI)

CDISC Submission Value	CDISC Definition
Withdrawal by parent/guardian	An indication that a study participant has been removed from the study by the parent or legal guardian
Withdrawal by subject	An indication that a study participant has removed itself from the study (NCI)

10.6. Appendix 6: Study Tabular Summary

CONFIDENTIAL

linaclotide

Parameter Group	Parameter	Value
Trial information	Study Title	A Phase 2, Randomized, Double-Blind, Placebo-Controlled, Sequential, Ascending, Multidose Study to Evaluate the Safety and Efficacy of Linaclotide in Pediatric Participants (Age 2 to 5 Years) with Functional Constipation.
	Clinical Study Sponsor	Allergan Sales LLC
	Study Phase Classification	2
	Study Indication	FC
	Study Indication Type	Study Intervention
	Study Type	Efficacy
		Safety
	Study Length	9 to 12 weeks per cohort
	Planned Country of Investigational Sites	United States and Canada
	Planned Number of Participants	up to 30
	FDA-Regulated Device Study	No
	FDA-Regulated Drug Study	Yes
	Pediatric Study	Yes
Participant information	Diagnosis Group	Children, Ages 2 to 5 Years with Functional Constipation
	Healthy Participant Indicator	No
	Planned Minimum Age of Participants	2
	Planned Maximum Age of Participants	5
	Sex of Participants	Both
	Stable Disease Minimum Duration	2 months (for participants aged ≥ 4 years old), or 1 month (for participants aged < 4 years old)

Parameter Group	Parameter	Value
Treatments	Study Intervention Therapy or Treatment	linaclotide
	Intervention Type	drug
	Pharmacological Class of Invest. Therapy	GC-C agonist
	Dose per Administration	 Cohort 1: linaclotide 18 μg or matching placebo once daily for 4-week Study Intervention Period. Cohort 2: linaclotide 36 μg or matching placebo once daily for 4-week Study Intervention Period. Cohort 3: linaclotide 72 μg or matching placebo once daily for 4-week Study Intervention Period. Final Cohort highest dose of linaclotide tested/determined to be safe or matching placebo for 4-week Study Intervention Period.
	Dose Units	μg
	Dosing Frequency	single dose, once daily at approximately the same time each day, 30 minutes prior to any meal.
	Route of Administration	Oral
	Current Therapy or Treatment	None
	Added on to Existing Treatments	No
	Control Type	Placebo
	Comparative Treatment Name	NA

Parameter Group	Parameter	Value
Study design	Study Type	Double-blind, placebo-controlled, Sequential, Ascending, Multidose Study to evaluate safety and efficacy
	Intervention Model	Sequential
	Planned Number of Groups	8 participants each in Cohorts 1 to 3, 6 participants in final cohort, study intervention and placebo in each cohort
	Study is Randomized	Yes
	Randomization Quotient	8 participants 3:1 linaclotide or placebo in Cohorts 1-3; 6 participants 5:1 linaclotide or placebo in final cohort
	Study Blinding Schema	Double blind
	Stratification Factor	None
	Adaptive Design	No
	Study Stop Rules	Monitoring of participant safety data will be performed by the DSMB. Study conduct may be interrupted or terminated by the sponsor based on DSMB recommendation or if, following a thorough review of all clinical, laboratory, and other available safety data, safety data become available which appear to represent an undue risk to the study participants' health or well-being.

10.7. Appendix 7: Instructions for Dosing

Four capsule strengths will be provided:

- 36 μg capsules, which are used to prepare the μg dose
- 72 μ g capsules, which are used to prepare the $\overline{18}$ μ g dose
- 145 μg capsules, which are used to prepare the 36 μg dose
- 290 μg capsules, which are used to prepare the 72 μg dose
- Placebo preparation is identical for all dose cohorts

Instructions for dose preparations are as follows: dose must be prepared at the time of administration and should not be prepared ahead of time and stored.

- 1. Pour exactly 20 mL of room-temperature bottled water into the provided medicine cup.
- 2. Open the capsule
- 3. Sprinkle the entire contents (beads) into the water
- 4. Gently swirl beads and water for at least 20 seconds.
- 5. Withdraw 5 mL into the provided oral syringe and discard this portion per instructions in the Study Reference Manual.
- 6. Withdraw a second portion of 5 mL into the oral syringe and administer dose to the participant, swallowing immediately.
- 7. Discard the remaining solution per instructions in the Study Reference Manual.
- 8. Rinse the syringe and medicine cup with bottled water.

Note that the drug is coated on the surface of the beads and will dissolve off the beads into the water. The beads will remain visible and will not dissolve. Therefore, it is not necessary to consume all the beads to deliver the complete dose.

10.8. Appendix 8: Study Schedule Supplement

The schedule of study procedures and assessments is tabulated by visit in the SOA in Section 1.3. The descriptions of the procedures to be performed at each visit are provided below.

10.8.1. Screening (Visit 1)

The Screening Period will occur 4 to 7 weeks before Randomization (Visit 3/Day 1) and last for 14 to 28 days during which time study procedures will be reviewed with the parent/guardian/LAR, and caregiver; and parent/guardian/LAR and caregiver consent will be obtained and documented (Section 10.1.3). After informed consent is obtained, participants will be registered in IWRS and assigned a unique PID number (Section 6.3). A review of inclusion/exclusion criteria and other screening assessments will be conducted to determine the participant's eligibility for enrollment (Sections 5.1 and 5.2).

At Screening (Visit 1) the following procedures will be performed:

- Review inclusion and exclusion criteria
- Complete modified Rome III assessment
- Register participants in IWRS
- Obtain medical history and current medication status
- Perform a physical examination, including: general appearance, skin, HEENT (head, ears, eyes, nose, and throat), neck, thorax/lungs, cardiovascular, abdomen, musculoskeletal, lymph nodes, neurologic (including mental status), and visual inspection of the lumbosacral and perianal region. Breast and genitourinary examinations are optional at the discretion of the investigator. Investigators should pay special attention to clinical signs related to previous serious illnesses.
- A fecal impaction assessment will be performed. Fecal impaction is defined as a hard mass in the lower abdomen identified on physical examination or a dilated rectum filled with a large amount of stool on rectal examination. If a rectal examination is performed, the medically qualified site personnel should assess for and document the presence of anal wink and normal anal tone. If fecal impaction is identified, participants will receive a dis-impaction regimen with either oral or rectal medication. The choice of treatment will be determined by the investigator after discussing the options with the participant and the caregiver. Options will include any over-the-counter or prescription laxative, suppository, or enema (eg, polyethylene glycol, lactulose, Fleet enema). After the participant has received treatment for the impaction, the investigator must re-evaluate the participant for the presence of fecal impaction at Visit 2/Preintervention Visit.
- Obtain height, vital signs (weight, temperature (oral, rectal, or tympanic), and respiratory rate), and postural vital signs (supine systolic and diastolic BP and pulse rate) (Section 8.2.2)

- Obtain standard 12-lead ECG (supine)
- Obtain clinical laboratory tests consisting of clinical chemistry, hematology, and urinalysis.
 All laboratory tests requiring blood draws should be collected at the same time
- Review any AEs occurring after informed consent is obtained

Additionally, during the Screening Period, caregivers will receive information about lifestyle modifications: increased water and fiber intake, increased physical activity, and consistent toileting habits. There should be at least a 2-week interval between discussing the lifestyle modifications during the Screening Period and the participant's entry into the Preintervention Period.

10.8.2. Preintervention Period (Visit 2)

The Preintervention Period (Visit 2) will occur 2 to 3 weeks before Randomization (Visit 3/Day 1) and last for 14 to 21 days. Participants will not receive study intervention during the Preintervention Period. If fecal impaction was documented during Screening (Visit 1), a fecal impaction assessment must be performed to determine continued eligibility for study participation. If there is no fecal impaction at Visit 2/Preintervention Visit, the participant may enter the Preintervention Period after adhering to any washout requirements. If fecal impaction is present upon re-examination, the participant will not be eligible for the study (ie, they have failed their out-patient clean-out regimen). If fecal impaction is documented during an optional repeat physical examination, the study physician must be notified.

Inclusion/exclusion criteria will be reviewed, caregivers will receive full training on the use and completion of the daily eDiary. IWRS registration will include rescue medication assignment (Section 6.5.2]). Caregivers will be instructed how to properly recognize signs of dehydration, how to administer oral rehydration therapy, and how to determine when the participant appears to be markedly ill or appears not to be responding to treatment for dehydration.

At the start of the Preintervention Period, caregivers will be trained in the use and completion of the eDiary including how to download eDiary responses and how to access the helpdesk if they encounter any problems using the eDiary.

Caregivers will be instructed to have the participant fast for at least 2 hours before receiving their first dose of study intervention at the study site during the Randomization Visit (Visit 3/Day 1)) and before their last dose of study intervention at the study site during Visit 5 (Week 4). Water will be allowed.

During the Preintervention Period (Visit 2), the following procedures will be performed:

Review inclusion and exclusion criteria

- IWRS verification
- Perform a fecal impaction assessment if fecal impaction was documented during screening (Section 10.8.1)
- Obtain vital signs (weight, temperature (oral, rectal, or tympanic), and respiratory rate) and postural vital signs (supine systolic and diastolic BP and pulse rate) (Section 8.2.2)
- Review any AEs occurring since the last visit
- Review concomitant medications
- Contact the IWRS, where applicable, for rescue medication to be dispensed to the participant.
- Remind caregiver to bring the bottle(s) of the rescue medication to the next visit.
- Instruct participants when to fast to ensure they have fasted for at least 2 hours before receiving the first dose of study intervention at the study site during the Randomization Visit; participants will be allowed to eat 30 minutes after dosing.
- Provide caregivers with the eDiary along with instructions

10.8.3. Randomization (Visit 3, Day 1)

Participants' eligibility to enter the Study Intervention Period must be confirmed prior to randomization by review of inclusion and exclusion criteria, including a fecal impaction assessment, adherence to instructions regarding the use of rescue medication and prohibited medications, meeting eligibility criteria captured in the eDiary device, including full compliance with eDiary on at least 10 of the 14 days immediately preceding Visit 3 and with clinic eDiary on the day of Randomization. The study coordinator will obtain the eDiary eligibility report to determine eDiary-related eligibility to be randomized. Once the participant's randomization eligibility is confirmed based on the eDiary eligibility report and other inclusion and exclusion criteria, the IWRS will randomize the participant. Study personnel will review the study procedures with the caregivers and instruct them to continue completing the eDiary entries every evening. Subsequent study visits will be scheduled keeping in mind that the last dose of study intervention will occur at Visit 5 and should occur at approximately same time as the other doses of study intervention during double-blind Study Intervention Period.

Randomization will occur on the first day of the Study Intervention Period. Based on randomization, participants will receive placebo or linaclotide. Participants will complete at least 4 weeks of treatment during the double-blind Study Intervention Period (ie, Study Intervention Period).

During the Randomization Visit (Visit 3), the following procedures will be performed:

• Review inclusion and exclusion criteria, including review of eDiary-related criteria

- IWRS verification
- Perform a fecal impaction assessment prior to randomization and dosing. If fecal impaction is present, the participant will not be eligible for the study.
- Obtain vital signs (weight, temperature (oral, rectal, or tympanic), and respiratory rate) and postural vital signs (supine systolic and diastolic BP and pulse rate) (Section 8.2.2)
- Review any AEs occurring since the last visit
- Review concomitant medications
- Review eDiary completion, including the Clinic eDiary
- Ensure participants have refrained from using rescue medicine on the prior calendar day and on the day of the Randomization (Visit 3) until the time of the clinic visit.
- Remind participants not to use rescue medicine for the remainder of the day and on the next calendar day after the Randomization Visit
- Run the eDiary Eligibility Report to confirm that the participant can be randomized.
- Review use of protocol-permitted rescue medication dispensed in IWRS where applicable.
 Participants may choose a different protocol-permitted rescue medication at any visit, where available. Additional protocol-permitted rescue medications may be dispensed as needed at any visit
- Prior to dosing, the investigator or appropriate site staff member will assess Rome IV criteria for childhood FC. Assessment result will be captured in the eCRF. Eligibility for the study is not based on this assessment
- Contact the IWRS to obtain the study intervention (bottle number) to be dispensed to the participant based on randomization and PK sample assignment.
- Prepare and administer the first dose of study intervention after completion of all Visit 3 assessments and after confirming the participant has fasted for at least 2 hours. Participants may resume eating 30 minutes after receiving their first dose of study intervention at the study site
- Dispense assigned study intervention for this study after the first dose has been administered. Provide study intervention reconstitution instructions for sprinkles to caregivers (Section 10.7).
- Record the date and time the first dose was administered

- Remind caregiver to bring the bottle(s) of the study intervention and rescue medication to the next visit
- Encourage caregivers to schedule Visit 5 (Week 4) as the participants will need to take linaclotide in a fasted state.

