4.5. End of Cohort Definition

The end of the cohort is defined as the date of the last visit of the last participant in the cohort or last scheduled procedure shown in the SoA for the last participant in the cohort globally.

5. Study Population

Prospective approval of protocol deviations to recruitment and enrollment criteria, also known as protocol waivers or exemptions, is not permitted.

Where applicable for this pediatric population, the term "participant" refers to the participant, parent, and/or caregiver.

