5.1. Inclusion Criteria

The targeted participant population will include male and female participants, 2 to 5 years of age. Participants are eligible to be included in the study only if all of the following criteria apply:

1.	Age and Weight
1.01	Male and female participants must be ages 2 to 5 years, (inclusive) at the time the parent/guardian/LAR has provided signed consent
1.02	Participant weighs $\geq 10~kg$ at the time the parent/guardian/LAR has provided signed consent
2.	Type of Participant and Disease Characteristics

2.01	Participant meets modified Rome III criteria for FC: For at least 2 months before Screening (Visit 1) (for participants aged ≥ 4 years old), or for at least 1 month before Screening (Visit 1) (for participants aged < 4 years old), the participant has had 2 or fewer defecations (with each defecation occurring in the absence of any laxative, suppository, or enema use during the preceding 24 hours) per week.		
	In addition, at least once per week, participant must meet 1 or more of the following:		
	a. History of retentive posturing or excessive volitional stool retention		
	b. History of painful or hard bowel movements (BMs)		
	c. Presence of a large fecal mass in the rectum		
	d. History of large diameter stools that may obstruct the toilet		
	e. At least one episode of fecal incontinence per week after the acquisition of toileting skills		
2.02	Participant is willing to discontinue any laxatives used before the Preintervention Visit in favor of the protocol- permitted rescue medicine.		
2.03	Participant has an average of fewer than 3 SBMs per week during the 14 days before the randomization day and up to the randomization (including the clinic eDiary assessments reported before administration of first dose of double-blind study intervention on the randomization day). An SBM is defined as a BM that occurs in the absence of laxative, enema, or suppository use on the calendar day of the BM or the calendar day before the BM		
2.04	Caregiver is compliant with eDiary requirements by completing daily assessments for 10 out of the 14 days immediately preceding the Randomization Visit.		
3.	Informed Consent		
3.01	Parent/guardian/LAR and caregiver must provide written informed consent before the initiation of any study-specific procedures		
3.02	Caregiver who will be completing the eDiary is able to read and/or understand the assessments in the eDiary device and must undergo training		

CONFIDENTIAL

linaclotide

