	motor, language, or social skills, which has a significant and continuing impact on the developmental progress of an individual) producing a cognitive delay that precludes comprehension and completion of the daily eDiary or other study-related questionnaires (Note: Participants are excluded if the person who will be completing the daily eDiary or other study-related questionnaires meets this criterion.)	
	k. Inflammatory bowel disease	
	Childhood functional abdominal pain syndrome	
	m. Childhood functional abdominal pain	
	n. Poorly treated or poorly controlled psychiatric disorders that might influence his or her ability to participate in the study	
	o. Lactose intolerance that is associated with symptoms which could confound the assessments in this study	
	p. History of cancer other than treated basal cell carcinoma of the skin. (Note: Participants with a history of cancer are allowed provided that the malignancy has been in a complete remission before the Randomization Visit. A complete remission is defined as the disappearance of all signs of cancer in response to treatment.)	
2.	Prior/Concomitant Therapy	
2.01	Participant used a protocol-specified prohibited medicine before the start of the Preintervention Period or failed to meet the stable-dose requirements of certain medications	
2.02	Participant used rescue medication on the calendar day before the Randomization Visit and on the day of the Randomization Visit until randomized	
2.03	Breastfeeding is allowed unless the mother is taking protocol-specified prohibited medicines (Section 6.5.1)	
	Prior/Concurrent Clinical Study Experience	
3.	Prior/Concurrent Clinical Study Experience	
3. 3.01	Prior/Concurrent Clinical Study Experience Participant received a study intervention during the 30 days before Screening (Visit 1) or is planning to receive study intervention (other than that administered during this study)	
	Participant received a study intervention during the 30 days before Screening (Visit 1) or	

4.02	Participant's parent/guardian/LAR or caregiver has been directly or indirectly involved in the conduct and administration of this study as an investigator, study coordinator, or other study staff member. In addition, any participant, parent/guardian/LAR or caregiver who has a first-degree family member, significant other, or relative residing with him/her directly or indirectly who is involved in this study

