6.5.2. Rescue Medication

In the United States and Canada, protocol-permitted rescue medication will be a choice of senna (oral), mineral oil enema (rectal), or magnesium hydroxide (oral) that will be dispensed according to the SOA (Section 1.3).

When there is more than one option available, the participants will choose a rescue medication(s) at the Preintervention Visit (Visit 2) and study site staff will register the rescue medication in IWRS, where applicable. The study site must contact the IWRS (if applicable) at all subsequent study visits to obtain the protocol-permitted rescue medication to be dispensed to the participant at each visit as needed.

Rescue medication may be taken when at least 72 hours have passed since the participant's previous BM or when their symptoms become intolerable.

Where available, the participant may continue using their original selection received from the study site throughout the duration of the study or may switch to another protocol-permitted rescue medication in coordination with the site staff

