### 16.3.4 Stool frequency

#### *Spontaneous Bowel Movement (SBM)*

A SBM is a BM that occurs in the absence of laxative, suppository, or enema use on the calendar day of the BM or the calendar day before the BM.

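### Protocol Sections 6.5.2 and 10.8.3 give opposing rescue-medication instructions for the rest of Day 1 and for Day 2, and no text says which governs

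*Protocol*

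**What the plan says.** Protocol Section 6.5.2 sets the conditions for rescue use: "Rescue medication may be taken when at least 72 hours have passed since the participant's previous BM or when their symptoms become intolerable". Either condition is enough. The section names no days on which rescue is barred and does not refer to Section 10.8.3.

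Protocol Section 10.8.3, the list of procedures for Visit 3 (Day 1), contains: "Remind participants not to use rescue medicine for the remainder of the day and on the next calendar day after the Randomization Visit". It gives no exception for either condition in 6.5.2. The opening of Section 5 explains that, where applicable, the term participant "refers to the participant, parent, and/or caregiver", so the instruction reaches the family.

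Two other provisions limit rescue around the same visit:
- Exclusion criterion 2.02 in Section 5.2: "Participant used rescue medication on the calendar day before the Randomization Visit and on the day of the Randomization Visit until randomized".
- An earlier item in the Section 10.8.3 list: "Ensure participants have refrained from using rescue medicine on the prior calendar day and on the day of the Randomization", up to the clinic visit.

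Both stop before the period at issue. The rescue footnote to the Schedule of Activities (Section 1.3) deals with dispensing and choice of product only. The SAP mentions no restricted days. Its Section 16.3.4 counts a BM as spontaneous only in the absence of laxative, "suppository, or enema use on the calendar day of the BM or the calendar day before the BM".

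**The concern.** The Section 10.8.3 item is worded as a reminder, which implies that the rule is set out somewhere else. It is not. For the rest of Day 1 and all of Day 2, one section permits what the other forbids, and no sentence ranks them.

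Three things are at stake.

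1. **Care.** The participants are 2 to 5 years old. A caregiver facing intolerable symptoms, or 72 hours without a BM, on either day has opposing instructions. The Schedule of Activities also lists rescue for dispensing at that visit.
2. **Compliance.** Protocol Section 8 makes adherence essential and allows no waivers, and SAP Section 8.0 summarizes significant protocol deviations. Whether rescue on Day 1 after dosing, or on Day 2, is a deviation cannot be determined from the text.
3. **Data.** SBM status depends on rescue use on the day of the BM or the day before. Inconsistent rescue use on Days 1 and 2 therefore carries into which BMs on Days 1 to 3 count as spontaneous.

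**Working it through.** The plan gives no figure on this point to reproduce. The main check is a comparison of the texts; the arithmetic only sizes the consequence.

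**Step 1. Coverage of each provision.**

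| Provision | Rest of Day 1 | Day 2 | Exception for 72 hours or intolerable symptoms |
|---|---|---|---|
| 6.5.2 | permits if a condition is met | permits if a condition is met | these are its conditions |
| 10.8.3 reminder | bars | bars | none stated |
| Exclusion 2.02 | silent (ends at randomization) | silent | none stated |
| 10.8.3 pre-dose check | silent (ends at the clinic visit) | silent | none stated |
| Schedule of Activities rescue footnote | silent | silent | none stated |
| SAP 16.3 | silent | silent | none stated |

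Only the first two rows speak to these days, and they disagree.

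**Step 2. Can the 72-hour condition be met inside the window?** There is no Day 0. The pre-visit limits and the reminder together cover Day -1, Day 1 and Day 2: 3 calendar days, or 3 × 24 = 72 hours. A child whose last BM fell before Day -1, with none since, meets the 72-hour condition no later than the end of Day 2, while the reminder still applies. Intolerable symptoms can arise at any time.

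**Step 3. How likely is a 72-hour gap?** The documents give no distribution of gaps. Criterion 2.03 bounds SBMs only: "Participant has an average of fewer than 3 SBMs per week during the 14 days before the randomization day". The 72-hour clock runs from any BM, and total BMs can exceed SBMs. As an assumption, take Poisson BMs at λ per week, so that P(no BM in a given 72 hours) = exp(−3λ/7):

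- λ = 1: 65%
- λ = 2: 42%
- λ = 3: 28%
- λ = 4: 18%
- λ = 5: 12%

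The range is too wide to support a count of affected children. It shows only that the situation is not exotic.

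**Step 4. Share of analysis days.** SAP 16.3.4 counts Day 1 as half a day. Week 1 = 0.5 + 6 = 6.5 days. With the last dose on Day 29, the period = 0.5 + 28 = 28.5 days. Rescue on both Day 1 and Day 2 removes SBM status from BMs on Days 1 to 3, which is 0.5 + 2 = 2.5 days: 2.5/6.5 = 38% of Week 1 and 2.5/28.5 = 9% of the period. These are shares of days, not effects.

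**Step 5. Effect on the mean SBM rate.** A deliberately heavy case: every child already at 72 hours takes rescue on both days, and all of that child's BMs on Days 1 to 3 lose SBM status. The mean loss in SBMs per week is then λ × (2.5/days in period) × exp(−3λ/7):

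| λ per week | 4-week rate | Week 1 rate |
|---|---|---|
| 1 | 0.088 × 0.651 = 0.06 | 0.385 × 0.651 = 0.25 |
| 2 | 0.175 × 0.424 = 0.07 | 0.769 × 0.424 = 0.33 |
| 3 | 0.263 × 0.276 = 0.07 | 1.154 × 0.276 = 0.32 |
| 4 | 0.351 × 0.180 = 0.06 | 1.538 × 0.180 = 0.28 |
| 5 | 0.439 × 0.117 = 0.05 | 1.923 × 0.117 = 0.23 |

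This leaves out children who reach 72 hours during the window and those who take rescue for intolerable symptoms, but it assumes full uptake among the rest. A simple day-level simulation with rescue used on 30 to 70% of eligible days (40,000 children per setting) gave a difference between the two rules of 0.04 to 0.07 SBMs per week in Week 1 and 0.02 or less over 4 weeks. Those values depend on how promptly rescue is assumed to produce a BM, so they indicate order of magnitude only.

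**The case against.** The strongest reply is that the texts can be read together. Section 6.5.2 is permissive, and Section 10.8.3 is a specific, short restriction. The protocol already places visit-related rescue limits outside 6.5.2, in exclusion 2.02 and the pre-dose check, so silence in 6.5.2 is weak evidence of conflict. Section 10.1.10 allows deviation when absolutely necessary for safety or clinical management, so the reminder is not absolute.

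Much of this stands. Reading 10.8.3 as an exception is plausible. It still leaves open whether that exception overrides the intolerable-symptoms condition. Section 10.1.10 only excuses a departure after the fact; it gives the caregiver no rule, and not every intolerable symptom clearly meets its threshold.

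The reply also disposes of several stronger readings a reader might infer:

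- *Identical stools would be classified differently between sites.* The SBM definition is common to all sites and depends on actual rescue use. Behavior may differ; classification does not.
- *Sites may choose which section to follow.* Appendix 8 directs every site to perform the Visit 3 procedures, including the reminder. The uncertainty lies in what families and investigators do when a 6.5.2 condition is then met.
- *A large, countable share of the 30 children is caught.* Thirty is a maximum, and the eligibility limit concerns SBMs while the clock runs from any BM. Step 3 shows how far the share moves.
- *The 4-week result is materially biased.* Step 5 does not support that. The instructions are the same in both arms, and all efficacy analyses are descriptive with no testing.

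**Conclusion.** The point holds as a minor internal inconsistency in the protocol. For the rest of Day 1 and for Day 2, Sections 6.5.2 and 10.8.3 give opposing instructions whenever a 6.5.2 condition is met, and no other text settles which applies or whether rescue then is a deviation. This conclusion rests on the wording alone and needs no assumption.

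The statistical consequence is slight: negligible for the 4-week SBM rate (0.02 per week or less with partial uptake, about 0.07 in the heavy case) and small for Week 1 (0.04 to 0.07 with partial uptake, up to about 0.33 in the heavy case). These sizes assume Poisson BMs and the stated rescue uptake, neither of which the documents supply. The reason to act is clear instruction to caregivers and consistent conduct. No view is taken here on which rescue rule is right.

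**What to change.** Reconcile Protocol Sections 6.5.2 and 10.8.3 so that one rescue rule covers Day 1 after randomization and Day 2. State that rule in 6.5.2, cross-refer to it from the 10.8.3 reminder, and say explicitly whether the 72-hour and intolerable-symptoms conditions apply on those two days. That will also settle whether rescue use then is a protocol deviation. The choice of rule is for the sponsor.

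The cost is about one sentence in 6.5.2, a cross-reference in 10.8.3 and a clarification letter to sites. No additional data and no SAP change are needed.
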